a. **Identify and flag unreliable cases:** The final step in the data screening process is to identify and flag entire cases (i.e., entire questionnaires) that are unreliable. By unreliable, we mean that we have sufficient reason to believe that the respondent's answers are not honest representations of their behaviors, knowledge, and beliefs. Cases are flagged as unreliable if the participant indicates they have not been honest in responding to the questionnaire or if project staff indicate in project logs specific issues encountered during data collection that are cause for treating a case as unreliable. Honesty during questionnaire administration is assessed from the following item on the *Participant Questionnaire*.

- *Have you been as honest as possible in responding to all of the questions in this questionnaire?*

Persons who indicate *No, none of the time* are flagged as unreliable. In addition, cases may be flagged as unreliable if project log notes indicate a notable issue during data collection (e.g., participant determined to be fraudulent). Each suspected unreliable case is reviewed by the project lead and a senior analyst for a final determination of reliability. Data for cases that are deemed unreliable are included in the benchmark analyses. However, sensitivity analyses that exclude the unreliable data will be conducted and results will be reported in an appendix of the report.

b. **Adjustment of baseline data:** In the final step of the data cleaning process, we determine if any individuals who are in the randomized sample (for each outcome) are missing baseline covariates or the baseline measure of the outcome variable. If this is the case, our proposed benchmark approach is to use dummy variable adjustment procedures, i.e., we code missing data to either zero or the mean of non-missing observations (for dichotomous and count/continuous variables, respectively). We construct dummy indicators to identify missing cases imputed to the constant/mean value and we adjust estimates by including these dummy indicators in analytic models.

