- a. Using data cleaning procedures outlined in the *Data cleaning* section, identify outlying, unreliable, and invalid data in any analytic (i.e., outcome, baseline, or covariate) variables. Recode invalid data as missing, and flag outlier and unreliable data for sensitivity analyses.²¹
- b. Report prevalence of unit and item missingness (which result from nonresponse and invalid data) for both treatment and control samples.²²
- c. Determine if logical edits are possible for any analytic variables that may have missing values (due to nonresponse) and logically update missing values where this is the case. We will not logically impute where the missing values are previously invalid.
- d. Determine if any individuals who are in the randomized sample (for each outcome) do not have outcome data at the follow-up time point. If this is the case, our proposed benchmark approach is to use case deletion, as we feel it is the most straightforward and prudent approach for missing follow-up data recommended in Puma et al. (2009). These cases will be deleted from the analytic sample and attrition statistics will be reported.
- e. Determine if any individuals who are in the analytic sample (for each outcome) are missing baseline covariates or the baseline measure of the outcome variable. If this is the case, our proposed benchmark approach is to use dummy variable adjustment procedures, as we feel it is the most straightforward and prudent approach for missing baseline/covariate data recommended in Puma et al. (2009).
- f. Conduct sensitivity analyses by estimating results with missing baseline data excluded from the analysis (i.e., use case-wise deletion for all cases with missing baseline and outcome data). In an appendix, we will report our benchmark results next to the sensitivity analysis results to verify findings.

²¹ We will code missing responses with a unique missing code that identifies or flags these missing values according to the reason they are missing (i.e., nonresponse, invalid, inconsistent). See the *Data cleaning* section for details on how missing data are coded.

²² For item missing values, we will only report prevalence of missing data for variables that are included in our model specifications and could therefore influence the constitution of the analytic sample.

b. Outcome measures

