In addition to the demographic variables, we will assess baseline equivalency of baseline measures of the outcome measures. We provide details on variable coding below; details on variable construction can be found in Table 2.

- *Frequency of having vaginal sex without condoms in the past 30 days* at baseline (continuous; values range 0 to k , where 0= has had vaginal sex without condoms 0 times in past 30 days and k = number of times having vaginal sex without condoms in past 30 days)
- *Current use of effective non-barrier contraception* at baseline (dichotomous; values of 0 or 1, where 0= not currently using effective non-barrier contraception and 1= currently using effective non-barrier contraception)
- *Number of sexual partners in the past 3 months* at baseline (continuous; values range 0 to k , where 0= has 0 sexual partners in past 3 months and k = number of sexual partners in past 3 months)

Balance Assessment Methods

We propose to assess baseline equivalence of the treatment and control groups according to a multi-step procedure. Baseline equivalence statistics will be produced for each analytic sample.³¹ Only participants who provide sufficient baseline and primary outcome data (i.e., non-missing) will be included in the test for baseline equivalence of the analytic sample for the specified outcome; thus, the analytic sample used for each research question may vary slightly because of the exclusion of non-responders.³² As required by the “Identifying Programs that Impact Teen Pregnancy, Sexually Transmitted Infections, and Associated Sexual Risk Behaviors” review protocol version 6.0, we will report the standardized mean difference of each baseline variable for the treatment and control groups.³³

To establish baseline equivalence, we propose to generate model-based point estimates of the difference between the treatment and control group means for the identified baseline equivalence variables. We will report the adjusted means of the difference in adjusted means of the baseline variable of interest for the treatment and control groups. We will then compute the pooled standard deviation of these variables. Finally, we will produce a standardized difference of means by dividing the first term by the second. The steps for establishing baseline equivalence using standardized mean difference are outlined below:

³¹ Due to item-missing outcome data, we expect there may be slight differences in analytic samples for each research question.

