³² Note that our benchmark approach is to produce diagnostic estimates of baseline equivalence on the sample of observations that have non-missing baseline and outcome data, without any adjustments to missing baseline data. We will conduct a sensitivity test, however, that calculates baseline equivalence using the exact same samples of observations that we will use in our primary analysis by applying the missing data approach outlined in *Data cleaning, subsection iv*.

³³ Mathematica Policy Research. (2022). Identifying Programs that Impact Teen Pregnancy, Sexually Transmitted Infections, and Associated Sexual Risk Behaviors: Review Protocol, Version 6.0.

step 1. First, we generate a model-based estimate of the difference between treatment and comparison groups on the baseline measures identified above. Separate models will be run for each of the baseline variables. The empirical model will be estimated with OLS (using Stata). If the measure is dichotomous, we propose to use a linear probability model to estimate the predicted probability of group membership. The model is a reduced-form variation of the model that we use to estimate program impact (as detailed in the *Model specification and covariates* section, below).³⁴

$$Y_{baseline} = \beta_0 + \beta_1 T + \sum (\beta_n D_n) + \varepsilon$$

where:

$Y_{baseline}$ – is the baseline measure of the variable that we use to establish baseline equivalency. This variable is included as a covariate in the benchmark analytic model (see Table 4 for details on variable coding). Separate models will be estimated for each baseline measure specified above.

β_0 – The intercept term, which represents the adjusted mean value of the baseline equivalency measure for participants in the control sample, with all other variables in the model held constant at zero.

β_1 – This represents the adjusted (but not standardized) mean difference in the baseline equivalency variable between treatment and control participants.

T - A dummy treatment indicator variable whose value equals 1 if the participant is randomized into the treatment group and zero otherwise.

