D – An n-1 vector of blocking variables (i.e., subgroups within which random assignment occurred), where n represents the full enumeration of all state by coordinator blocks from which participants were randomly assigned to a condition. For each of these n coordinator-by-state blocks, we include in the baseline equivalence model a dummy indicator variable that will identify whether a study participant was randomized within that block (1) or not (0).

ε – The residual or random variation that remains for each observation after the structural components of the model are estimated. It is the difference between the observed and the predicted values at the individual level.

step 2. Report the adjusted means of the differences in the baseline variable of interest for the treatment and control groups.

step 3 (continuous variables only). If the baseline measure is continuous, we propose to use the following formula to calculate the pooled within-group standard deviation of the outcome measure:

³⁴ It is a reduced-form because individual-level, demographic covariates are omitted. It is a variation because the dependent variable is the baseline equivalence variable, not the outcome measure.

$$S_p = \sqrt{\frac{(n_t - 1)S_t^2 + (n_c - 1)S_c^2}{(n_t + n_c - 2)}}$$

where: n_t and n_c are the sample sizes, and S_t and S_c are the participant-level standard deviations for the baseline measures for the analytic treatment and comparison groups, respectively. We will produce separate calculations of the pooled standardized deviation for each variable used to establish baseline equivalence (as noted above).

step 4. Produce the standardized difference of means. If the pre-intervention measure is continuous, we will use the formula for Hedges' g to compute the standardized difference of means for the treatment and comparison groups:

$$g = \frac{\beta_1}{S_p}$$

where: β_1 is the adjusted mean difference in the variable selected to establish baseline equivalence for the treatment and comparison groups (calculated in Step 1), and S_p is the pooled standard deviation (produced in Step 3).

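### Footnote 32's sensitivity balance check fills missing values of the variable being tested, which distorts the standardised differences it reports

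*SAP*

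**What the plan says.** Section 4.d sets out two balance checks. In the benchmark version, "Only participants who provide sufficient baseline and primary outcome data (i.e., non-missing) will be included in the test for baseline equivalence"; footnote 32 describes this as the "sample of observations that have non-missing baseline and outcome data, without any adjustments to missing baseline data". Footnote 32 then adds a sensitivity version that "calculates baseline equivalence using the exact same samples of observations that we will use in our primary analysis by applying the missing data approach" of section 4.a.iv.

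On incomplete baseline variables, step e of section 4.a.iv states: "our proposed benchmark approach is to use dummy variable adjustment procedures, as we feel it is the most straightforward and prudent approach for missing baseline/covariate". Section 4.a.iii.b gives the fill values: "we code missing data to either zero or the mean of non-missing observations (for dichotomous and count/continuous variables, respectively". It adds that "we adjust estimates by including these dummy indicators in analytic models".

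The balance model in step 1 of section 4.d regresses the baseline variable on the treatment indicator T and the block dummies D. Footnote 34 says of this model: "It is a variation because the dependent variable is the baseline equivalence variable, not the outcome measure". The equation has no missing-data indicator M. For continuous variables, step 4 says "we will use the formula for Hedges' g to compute the standardized difference of means for the treatment and comparison groups", as the coefficient of T divided by the pooled SD. For dichotomous variables the Cox index is the difference in log odds divided by 1.65. Neither formula is adapted for filled values.

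**The concern.** Filling with a constant and adding a missing indicator is a way to keep people in a regression when a right-hand-side covariate is missing. The indicator absorbs the arbitrary constant, and the treatment coefficient for the outcome stays usable. In the balance check the incomplete variable is on the left-hand side. People with filled values carry no information about it, yet each adds a zero or the overall mean to the arm's average.

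Any gap between the sensitivity check and the benchmark would then partly reflect the fill values rather than a baseline difference between arms. This is the only planned balance check on the exact sample behind each primary estimate, so a reader would take it as evidence on whether that sample is balanced.

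**Working it through.** The SAP states no missing rate, prevalence or balance statistic, so there is no figure to reproduce. The formulas below are the SAP's. Missing shares, prevalences and true differences are assumptions, with missingness at random within arm and 1:1 allocation.

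**Yes/no variables, zero fill, arms truly identical.** With prevalence p and missing share m, the filled proportion is p(1 - m) in each arm, and Cox = [logit(p_t) - logit(p_c)] / 1.65. For p = 0.5 with 5% (treatment) v 10% (control) missing:
- filled proportions: 0.475 and 0.450, a difference of 0.025
- logits: -0.1001 and -0.2007
- Cox = 0.1006 / 1.65 = 0.061

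| Missing, treatment v control | p = 0.2 | p = 0.5 | p = 0.7 | p = 0.9 |
|---|---|---|---|---|
| equal (2%, 5% or 10% in both) | 0.000 | 0.000 | 0.000 | 0.000 |
| 1% v 3% | 0.015 | 0.024 | 0.039 | 0.105 |
| 2% v 5% | 0.023 | 0.036 | 0.058 | 0.144 |
| 5% v 10% | 0.040 | 0.061 | 0.093 | 0.197 |

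False imbalance therefore needs missingness that differs by arm, and it is largest for traits that most participants have.

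**Yes/no variables, zero fill, real imbalance, equal missingness.** The same formula gives:

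| True proportions | none missing | 5% | 10% |
|---|---|---|---|
| 0.55 v 0.50 | 0.122 | 0.115 | 0.109 |
| 0.92 v 0.88 | 0.273 | 0.187 | 0.142 |

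Here the fill shrinks a true difference.

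**Counts, mean fill.** With equal m in both arms, the arm difference is multiplied by (1 - m) and the SD by about sqrt(1 - m), so g is multiplied by about sqrt(1 - m). For a true g of 0.25 (SD 1) and m = 10%:
- difference: 0.25 × 0.90 = 0.225
- variance: 0.90 + 0.90 × 0.10 × 0.125² = 0.9014, so SD = 0.9494
- g = 0.225 / 0.9494 = 0.237

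| True g | 2% missing | 5% | 10% | 20% |
|---|---|---|---|---|
| 0.25 | 0.247 | 0.244 | 0.237 | 0.223 |
| 0.10 | 0.099 | 0.098 | 0.095 | 0.089 |

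**Adding M to the balance model.** A simulation with 2,000,000 observations compared the OLS coefficient of T with and without M:
- Identical arms, p = 0.9, 5% v 10% missing: 0.0446 without M and -0.0003 with M. The false difference disappears.
- Proportions 0.92 v 0.88, 10% missing in both arms: 0.0364 either way, against a true 0.040.
- Continuous, true difference 0.25, 10% missing in both arms: 0.2249 either way.

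M removes the false yes/no difference from the coefficient but not the dilution. A Cox index computed from the filled proportions would remain distorted, since its formula has no place for M.

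**The case against.** The strongest reply has four parts.

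- **M may be intended.** Footnote 32 invokes the whole missing-data approach, which includes the indicators, and the SAP does not say that M is left out of the sensitivity version. This stands in part: the printed equation has no M, and adding it would leave the dilution and the Cox problem.
- **Exposure is limited.** Under section 2.a.ii a person joins the ITT sample only after completing the baseline questionnaire, so item nonresponse and invalid values are the main sources of missingness. Participants learn their arm only after submitting it. Age comes from the screening form. Table 4 codes non-selection as 0 for gender and Hispanic/Latino, so read literally the fill adds nothing there; current contraceptive use is the clear case. This stands. Arm differences could still arise by chance, through follow-up response, or through coordinators, who see the allocation while the participant completes the baseline.
- **Missingness by arm is already reported** under step b of section 4.a.iv. This stands; what is lacking is its place in the balance table.
- **Nothing depends on the check.** It is a sensitivity test of a diagnostic, with no threshold or decision attached. This also stands, and it keeps the point minor.

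A reader might infer that the check always produces false imbalance for yes/no variables and hides imbalance for counts. The SAP's formulas do not support that: with equal missingness and identical arms the Cox index is exactly zero, and g falls only from 0.25 to 0.223 even at 20% missing. Nor does the point extend to the impact models, where the filled variables are covariates and M is included.

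**Conclusion.** The point holds as a minor error in the plan as written. Followed literally, footnote 32 fills the dependent variable of the balance model and so reports distorted standardised differences. For yes/no variables the direction depends on missingness: false imbalance if it differs by arm, shrinkage of real imbalance if it is equal. For counts the effect is dilution of about 2.5% of g at 5% missing, 5% at 10% and 11% at 20%.

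The size rests on missing rates and prevalences that the SAP does not give. At low missingness it is negligible. The larger Cox values (0.105 to 0.197) require unequal missingness and a prevalence near 0.9, and nothing in the SAP shows that prevalence for contraceptive use. The benchmark balance check and the impact estimates are untouched.

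**What to change.** Reword footnote 32 so that, for the impact sample of each primary outcome, each standardised difference uses all observed values of that baseline variable. The variable under test is not filled, and nobody is dropped because a different baseline item is missing.

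In the same balance table, add one row per baseline variable for its missing-data indicator: the share missing in each arm, with a Cox index where it can be calculated. The item-missingness counts planned in step b of section 4.a.iv supply these figures.

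If the benchmark is already run variable by variable on non-missing values, the unfilled differences will largely repeat it, and the indicator rows are the real addition.

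The cost is one reworded footnote and a few table rows. Data collection, the benchmark balance check and the impact models do not change.

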X – A p vector of baseline (i.e., measured prior to receiving intervention or exogenous to treatment) participant-level covariates to account for the variation in outcomes associated with these groups. These covariates, listed in detail in Table 4, will include:

- a) Age – self-reported age (based on date of birth) at screening (continuous; range 16-21); variable will be re-centered at the grand mean for analysis.
- b) Gender – gender of participants as self-reported at baseline (coded as 1 if female and coded as 0 if otherwise); variable will be re-centered at the grand mean for analysis.
- c) Race – race of participant as self-reported at baseline (coded as 1 if participant self-identified as only White and 0 if otherwise); variable will be re-centered at the grand mean for analysis.
- d) Ethnicity – Hispanic/Latino(a) ethnicity of participant as self-reported at baseline (coded as 1 if identify as Hispanic/Latino(a) and 0 if do not identify as Hispanic/Latino(a)); variable will be re-centered at the grand mean for analysis.

D – An $n-1$ vector of blocking variables (i.e., subgroups within which random assignment occurred), where n represents the full enumeration of all state-by-coordinator blocks from which participants were randomly assigned to condition. For each of these n coordinator-by-state blocks, we include in the analytic model a dummy indicator variable that will identify whether a study participant was randomized within that block (1) or not (0). The variables will be re-centered at the grand mean for analysis.

M – A p vector of missing baseline data indicator variables representing each of the p baseline covariates that had missing observations (coded as 1 if the observation for that variable is missing and 0 if it is non-missing).

Using a vector of dummy variables (LSDV) in a regression to account for a blocked randomization scheme is a conventional choice for a situation where each block has the same probability of assignment.³⁶ This is consistent with our design specification and so we have adopted the dummy variable modeling strategy here. As Angrist (1998) and others have pointed out, however, scenarios exist where the strategy may fail to identify the estimand of interest for a variety of reasons. Of particular interest

³⁶ Gerber, A. S., & Green, D. P. (2012). *Field Experiments: Design, Analysis and Interpretation*. W.W. Norton & Company.

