here is that the dummy-blocking scheme may exclude blocks/cases from the full randomized sample. Regardless of what the nominal randomization probabilities may be, one feature of the blocking model is that it will assign zero weight to any block partition where the actualized probability of treatment equals 0 or 1. That is, study assignment blocks that contain only a single participant (who is then assigned to either treatment or control) are functionally excluded from the treatment effect estimate.

If this is pervasive enough in the analytic sample – where multiple cells exist with just a single participant – impact estimates may fail to identify the treatment effect for the fullest possible ITT sample. In this case we will alter our benchmark approach and substitute the LSDV procedure with an almost-equivalent inverse-probability-of-treatment-weighted (IPTW) regression, which should mitigate the exclusion problem, while still weighting cells accordingly. This estimation approach is almost equivalent to the LSDV blocking procedure except that it is functionally saturated with respect to the treatment and dummy variables (but not covariates), and it can be constructed to broaden the analytic sample to include cells where only a single case was randomized and (calculated) probability of treatment is 0 or 1.³⁷ When we use a normalized IPTW and estimate the propensity score with the linear probability model the single-case blocks are given reduced but not zero weight.

If we use the IPTW regression as the benchmark approach, we will weight each observation by the inverse probability of assignment for their condition in their block. For the treatment group, the weights will be $\frac{1}{e(x)}$; for the control group, weights will be $\frac{1}{1-e(x)}$. Where $e(x)$ is the propensity score estimated by the linear probability model using the following specification:

$$e(x) = \alpha_0 + \sum (\beta_n D_n) + \varepsilon$$

Prior to estimation we will normalize weights such that the sum of all weights will be equal to 1.

We will report model-estimated effects and the results of significance tests in the findings section of the final impact report. Statistical significance will be based on test statistics produced by Stata for the coefficient β_1 using a two-tailed test, with $p < .05$.

ii. Adjustment for baseline differences

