- i. **Difference of means.** Our benchmark approach is to include baseline covariates and blocking variables in an OLS regression model to improve the precision of our effect estimates. Assuming our sample is sufficiently large, this approach should generate unbiased estimates.⁴⁴ To test this, we will conduct sensitivity analyses that use OLS and only the treatment indicator included as an independent variable. This approach should approximate a difference of means t-test. We will report any substantive differences in the results section of the final manuscript and analytic findings for both approaches will be presented alongside each other in an appendix.
- ii. **Alternative models.** Our benchmark approach includes covariates and accounts for blocking procedures either using fixed effects for the study coordinator-by-state assignment blocks or an IPTW approach that is similar but does not zero-weight single-case cells. This strategy offers a compromise between the unbiasedness of the difference-of-means approach and the added precision and statistical power offered by regression adjustment. Heterogeneous treatment effects, however, remain a possible threat to this approach. As such, we propose to fit a model that constructs a treatment effect from a weighted average of a fully saturated OLS regression model. We will use the weighted least squares version of this model proposed by Lin (2013, p.10). We will report any substantive differences in the results section of the final manuscript and analytic findings for both approaches will be presented alongside each other in an appendix.
- iii. **Without baseline covariates.** Our benchmark approach is to include baseline covariates in our model to improve the precision of our estimates. To test this, we will conduct sensitivity analyses that involve running identical empirical models without the baseline covariates included. We will report any substantive differences in the results section of the final manuscript and analytic findings for both approaches will be presented alongside each other in an appendix.

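### The default primary model gives no weight to one-arm state-by-coordinator blocks, and the switch that would bring them back has no defined trigger

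*SAP*

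**What the plan says.** Section 4.e.i (Estimation approach) sets the default as OLS with block dummies (LSDV), "where n represents the full enumeration of all state-by-coordinator blocks from which participants were randomly assigned to condition". The Introduction and Table 4 put the maximum at 255 blocks.

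The same section then states the model's weakness: "it will assign zero weight to any block partition where the actualized probability of treatment equals 0 or 1". Its next sentence restates this as a matter of blocks holding one person.

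The remedy is a conditional change of benchmark. The condition is "If this is pervasive enough in the analytic sample", explained only as "where multiple cells exist with just a single participant". If it is met, the plan will "substitute the LSDV procedure with an almost-equivalent inverse-probability-of-treatment-weighted (IPTW) regression". Under IPTW, the SAP says, "the single-case blocks are given reduced but not zero weight".

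Significance for each primary outcome is read from the single treatment coefficient, two-sided at .05. Section 4.f carries the approach over to the full-sample secondary outcomes. Section 4.g.ii still describes the benchmark as one that "accounts for blocking procedures either using fixed effects for the study coordinator-by-state assignment blocks or an IPTW approach". The baseline-equivalence model in section 4.d does not mention the switch: "For each of these n coordinator-by-state blocks, we include in the baseline equivalence model a dummy indicator variable".

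**The concern.** With up to 255 blocks, many may hold one analyzed participant, or a few who are all in the same arm. The default model then discards those people from the treatment comparison while still spending a parameter on each block. The SAP sees this, but leaves the remedy to a judgment with no number, no date and no stated quantity to count.

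Two analysts following the text could name different models as primary. The models weight participants differently and can differ in power. The condition is assessed in the analytic sample, which exists only after cases with missing outcomes are deleted (section 4.a.iv) and which the SAP expects to differ slightly between outcomes (section 4.d). So the three primary outcomes could even end up with different models.

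**Working it through.** **1. Block count.** 51 states × 5 coordinators = 255, as the SAP states. It gives no sample size, power or threshold to reproduce.

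**2. What LSDV discards.** Leaving covariates aside, the LSDV estimate averages the within-block differences with weight n·e·(1−e), where n is the block size and e its treated share.
- Four people, two per arm: 4 × 0.5 × 0.5 = 1.
- One treated person: 1 × 1 × 0 = 0.
- Two people, both treated: 2 × 1 × 0 = 0.

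The SAP's general rule is therefore right. Its gloss is too narrow, because one-arm blocks of two or more are lost as well.

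**3. What IPTW keeps.** With e equal to the block's treated share, a two-arm block has total weight n_t(n/n_t) + n_c(n/n_c) = 2n, or 2 per person on average. In a one-arm block each person has weight 1/1 = 1. Every one-arm block is kept at reduced weight, whatever its size.

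**4. Planned comparisons.** Section 4.g lists eight sensitivity analyses: treatment indicator only, saturated weighted model, no covariates, no baseline adjustment, no unreliable cases, no outliers, condensed windows, and count or logit models. None sets LSDV beside IPTW.

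**5. Power, by simulation (all settings assumed).** 7, 25 or 51 states; 300, 500 or 900 randomized; 15% missing outcomes; state sizes proportional to rank^−0.8; coordinator shares 30/25/20/15/10%; permuted blocks of 2, 4 and 6; overdispersed counts with mean 5 and a correlated baseline; a true 25% lower mean; robust standard errors; 4,000 trials per setting. With 7 states, power differed by at most 2 points. Otherwise (power, %):

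| States | Randomized | LSDV | IPTW | Additive dummies | LSDV shortfall (points) |
|---|---|---|---|---|---|
| 25 | 300 | 28.6 | 41.0 | 42.7 | 12.4 / 14.1 |
| 25 | 500 | 58.6 | 65.8 | 67.3 | 7.2 / 8.7 |
| 25 | 900 | 86.9 | 87.8 | 88.9 | 0.9 / 2.0 |
| 51 | 300 | 17.0 | 40.7 | 43.2 | 23.7 / 26.2 |
| 51 | 500 | 42.6 | 61.3 | 64.6 | 18.7 / 22.0 |
| 51 | 900 | 81.8 | 86.8 | 88.3 | 5.0 / 6.5 |

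A second simulation under similar assumptions gave LSDV/IPTW/additive power of about 34/48/46% (25 states, 300), 48/70/72% (51 states, 500) and 87/92/92% (51 states, 900), with no loss at 7 states. A third, with normal outcomes, no effect and all 51 states open, found the SD of the LSDV estimate 17–44% above that of IPTW at 200 randomized and 4–6% above at 800.

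Part of the power loss is overstated standard error. At 51 states and 500, the LSDV standard error is 1.28 times the additive one, while its true SD is 1.16 times.

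**6. Would the switch be made?** Analyzed = 0.85 × randomized. The share is the mean number of single-participant cells divided by that.

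| States | Randomized | Analyzed | Single cells | Share |
|---|---|---|---|---|
| 25 | 300 | 255 | 35 | 13.7% |
| 25 | 500 | 425 | 27 | 6.4% |
| 25 | 900 | 765 | 14 | 1.8% |
| 51 | 300 | 255 | 71 | 27.8% |
| 51 | 500 | 425 | 74 | 17.4% |
| 51 | 900 | 765 | 62 | 8.1% |

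Read as two or more such cells, the condition is met in every trial in all six settings. Read as a share, the answer depends on the cut. At 51 states and 500 randomized, a 10% cut is met in 100% of trials and a 20% cut in 6%. What is counted matters too: at 51 states, 900 randomized and a 10% cut, single-participant cells meet it in 2% of trials and all one-arm blocks in 96%.

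**7. Type I error.** With no effect, LSDV rejected in 1.9–5.6% of trials, and at least one of the two models in 4.8–6.5%. In the normal-outcome simulation, taking the smaller p-value gave about 4–6%.

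**The case against.** The plan is not indifferent between two models. It names LSDV as the default, names one replacement with its weight formula, and says what problem the replacement answers. The wording in section 4.g.ii only restates that rule. This stands: the gap is an undefined switch away from a weak default, not two equal benchmarks.

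Read literally, more than one single-participant cell would trigger IPTW in every many-state setting above, and then no power is lost. This also stands. The 10% and 20% cuts are illustrations that appear nowhere in the SAP. But the sentence makes pervasiveness the condition, so a stricter reading is equally open.

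Section 4.g.i commits to a treatment-only regression shown beside the benchmark, which keeps everyone. That is partial cover. It drops covariates and blocks together, so a difference from the benchmark could not be traced to the discarded blocks.

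A reader might infer that the analysts could pick the favorable p-value and inflate the error rate. The documents do not support that: the criterion concerns cell counts, not effects, and the simulated error stays near 5%. A reader might also infer that the counts were known when the plan was written, since enrollment closed in April 2023. Randomized block sizes could be tallied then. The condition refers to the analytic sample, however, and the primary follow-up falls four months after baseline, so those cells could not have been final in June 2023, the date on the plan body.

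The baseline-equivalence model is called a reduced variant of the impact model, so it can be read as following the switch. That mismatch is minor.

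**Conclusion.** The point holds in this limited form and should be fixed. The default primary model discards participants the trial randomized and measured, and the step that would restore them rests on an unquantified condition, described more narrowly than the problem it addresses.

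Neither model is biased, since assignment is .5 in every list (section 2.a.iii), and type I error is not meaningfully raised. The loss is in precision and prespecification. It is negligible if about seven states contribute, and roughly 1 to 25 power points with 25 to 51 states and 300 to 900 randomized, if LSDV is kept.

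These figures rest on an assumed sample size, state spread, missingness and effect, and on a count outcome; the binary outcome was not simulated. A wide spread is plausible: by footnote 7 of the SAP, eligibility opened in December 2021 to any state with the partner's health centers, which covers 17 of the 23 enrollment months. The number of states that actually contributed is not given. The textual gap does not depend on any of these assumptions.

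**What to change.** Before outcome data are examined, remove the trigger and name one benchmark that keeps every analyzed participant, for all three primary outcomes. Either choice is sound:

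- the SAP's own IPTW regression, with block dummies left out of the weighted outcome model. The SAP implies this but does not write the equation, and keeping the dummies brings the loss back (45.4% power instead of 61.3% at 51 states and 500 randomized);
- OLS with additive state and coordinator dummies.

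Report full-block LSDV beside it as a sensitivity analysis, and compute baseline equivalence with the benchmark's weighting. Setting e(x) to the design value of .5 in one-arm blocks is optional, worth about 0 to 3 power points.

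The cost is one paragraph of SAP text. The small downside is that the benchmark no longer conditions fully on each state-by-coordinator block; with equal assignment probability in every list this causes no bias.
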